5.8 Duration of Therapy

In the absence of treatment delays due to adverse events, treatment may continue until completion or protocol-defined therapy or until:

- Disease progression after Day 15 of Cycle 1
- Inter-current illness that prevents further administration of treatment
- Unacceptable adverse event(s)
- Patient decides to withdraw from the study, **OR**
- General or specific changes in the patient's condition render the patient unacceptable for further treatment in the judgment of the investigator.

5.9 Duration of Follow Up

Patients will be followed every 3 months for a minimum of **2 years** after removal from or completion of treatment or until death, whichever occurs first. Patients removed from treatment for unacceptable adverse events will be followed until resolution or stabilization of the adverse event then for relapse and survival afterwards.

6. STUDY PROCEDURES

6.1 Screening/Baseline Procedures

Assessments performed exclusively to determine eligibility for this study will be done only after obtaining informed consent. Assessments performed for clinical indications (not exclusively to determine study eligibility) may be used for baseline values even if the studies were done before informed consent was obtained.

All screening procedures must be performed within 21 days prior to registration unless otherwise stated. The screening procedures include:

6.1.1 Informed Consent

The investigator or their designee must obtain documented consent from each potential subject prior to participating in a clinical trial.

Consent must be documented by the subject's dated signature or by the subject's legally acceptable representative's dated signature on a consent form along with the dated signature of the person conducting the consent discussion.

A copy of the signed and dated consent form should be given to the subject before participation in the trial.

The initial informed consent form, any subsequent revised written informed consent form and any written information provided to the subject must receive the IRB/ERC's approval/favorable opinion in advance of use. The subject or his/her legally acceptable representative should be informed in a timely manner if new information becomes available that may be relevant to the subject's willingness to continue participation in the trial. The communication of this information will be provided and documented via a revised consent form or addendum to the original consent form that captures the subject's dated signature or by the subject's legally acceptable representative's dated signature. The informed consent will adhere to IRB/ERC requirements, applicable laws and regulations and Sponsor requirements.

Copy of signed informed consented to be faxed [contact]) or emailed via secure email ([contact]) to UCSD.

6.1.2 Medical history

Complete medical, surgical and oncology history as well as history of infections are obtained at screening. Any changes from Screening (e.g. worsening severity or abnormal findings) are considered to be adverse events (AEs).

6.1.3 Demographics

Demographic profile will include date of birth, gender, race, and ethnicity.

6.1.4 Review subject eligibility criteria

Review of eligibility criteria as described in **Section 4** to ensure subject qualification for study entry.

Prior to assignment of patient study ID the below items must be emailed via secure email to the initiating site for review and approval.

1. Signed informed consent
2. Redacted source documentation required to confirm eligibility (including but not limited to):
 - a. Bone marrow biopsy report
 - b. Physical exam including ECOG and medical history
 - c. All screening labs
 - d. Chest X-Ray results
 - e. Confirmation of sample to foundation one
3. Signed eligibility criteria (**Appendix D**)

All items to be emailed via secure email to ([contact] and [contact]) to UCSD.

Upon receipt of all required documents, UCSD will provide subsite with patient ID and approval to initiate treatment

6.1.5 Review previous and concomitant medications

All prior medication taken by the subject within 4 weeks before starting the study is to be recorded. Concomitant medications taken by the subject during the study are to be recorded up until 28-days after last study dose. If a reportable adverse event (see **Section 8**) occurs within 28-days after last study dose, recording of concomitant medications should continue until resolution of the adverse event.

6.1.6 Physical exam including vital signs, height and weight

Vital signs (temperature, pulse, respirations, blood pressure), height (only required at screening), and weight. Physical exam to include neurological per institutional standard of care and testicular exam.

6.1.7 Performance status

ECOG performance status evaluated at screening and with every physical exam.

6.1.8 Adverse event assessment

Baseline assessment of subject status for determining adverse events. See **Section 8** for Adverse Event monitoring and reporting.

6.1.9 Hematology

Complete Blood Count (CBC) with differential.

6.1.10 Serum chemistries:

Comprehensive metabolic panel (CMP) to include: albumin, alkaline phosphatase, ALT/SGPT, AST/SGOT, BUN, creatinine, electrolytes (sodium, potassium, calcium, chloride, bicarbonate), glucose, and total bilirubin. Additional chemistries: lactate dehydrogenase (LDH), uric acid, magnesium, phosphate, TSH, T4, direct bilirubin, amylase and lipase.

6.1.11 Coagulation

Coagulation profile includes International Normalized Ratio (INR), prothrombin time (PT) and activated partial thromboplastin time (PTT).

6.1.12 Hepatitis B, Hepatitis C and HIV serologies

Hepatitis B surface antigen, hepatitis B surface antibody, hepatitis B core antibody total, hepatitis C antibody, and HIV-1/2 Antibodies

6.1.13 Pregnancy test (for females of child bearing potential)

See **Section 4.1.9** for definition.

6.1.14 Lumbar Puncture with CSF assessments and initiation of intrathecal Methotrexate

If WBC >10,000/mcl delay procedure until WBC <10,000/mcl. CSF studies: Cell count with differential, total protein, glucose and cytology.

Intrathecal methotrexate 15 mg once

6.1.15 Disease assessment

Bone marrow aspirate and biopsy to include standard morphology, flow cytometry, karyotype, and *in situ* hybridization for t(9;22)(q34;q11.2)[BCR-ABL1]; t(v;11q23)[MLL rearranged]; t(12;21)(p13;q22)[ETV6-RUNX1]; t(1;19)(q23;p13.3)[TCF3-PBX1].

Institutional ALL FISH panel supercedes. Quantitative PCR for BCR-ABL1 p190 and p210 isoforms.

Collection of bone marrow correlative studies (see **Section 6.5** for details).

6.1.16 Molecular testing (FoundationOne™ Heme testing)

See **Section 6.5.1.1** for details of collection procedures.

6.1.17 Statement of Planned Allogeneic HCT

Form located in **Appendix E** to be completed and faxed or emailed via secure email to UCSD prior to starting treatment

6.1.18 Imaging

PET-CT (preferred) with diagnostic CT chest, abdomen, and pelvis with IV and oral contrast in patients with palpable lymphadenopathy or tumor masses. Patients unable to get a contrast-enhanced study should get non-contrast enhanced CT scans. If PET is not possible due to patient instability, institutional restrictions, or risk of delaying therapy then subject should undergo CT of the chest, abdomen, and pelvis without PET.

6.2 Procedures During Treatment

Lumbar puncture with intrathecal methotrexate 15 mg day 29 + 8 days during cycles 1-4 and day 38 + 8 of cycle 5 for total of 6 doses including dose given at screening. CSF studies with each lumbar puncture: Cell count with differential, cytology, and flow cytometry.

Adverse events and concomitant medications to be collected continuously while on study.

Cycle 1

Day 1

Collection of Serum Cytokine Assay samples (See **Section 6.5**) prior to blinatumomab

Administration of Blinatumomab 9 mcg/d CIV on days 1-7 (hospital admission required per section 5.1.3)

Physical exam, performance status, vital signs, weight

Vital signs (heart rate and oxygen saturation) to be monitored continuously and full vital signs (temperature, heart rate, blood pressure, respiratory rate, and oxygen saturation) every 4 hours during at least the initial 72 hours of blinatumomab therapy, for 72 hours after all restart or step-up doses, and for at least the initial 72 hours following the first (Cycle 1, Day 15).

Labs: CBC with differential, CMP (sodium, potassium, chloride, bicarbonate, BUN, creatinine, glucose, calcium, total bilirubin, AST, ALT, alkaline phosphatase), direct bilirubin

Adverse Event Assessment

Concomitant Medications

Day 2

Collection of Serum Cytokine Assay Samples 24 hours +/- 2 hour after start of blinatumomab (See **Section 6.5**)

Day 3

Collection of Serum Cytokine Assay samples 48 hours +/- 2 hours after start of blinatumomab (See **Section 6.5**)

Day 8

Collection of Serum Cytokine Assay samples (See **Section 6.5**) prior to increase in blinatumomab dose

Start administration of Blinatumomab 28 mcg/d CIV days 8-28

Day 9

Collection of Serum Cytokine Assay Samples 24 hours +/- 2 hour after start of blinatumomab 28 mcg/day (See **Section 6.5**)

Day 10

Collection of Serum Cytokine Assay samples 48 hours +/- 2 hours after start of blinatumomab 28 mcg/day (See **Section 6.5**)

Day 14

Labs: CBC with differential, CMP (sodium, potassium, chloride, bicarbonate, BUN, creatinine, glucose, calcium, total bilirubin, AST, ALT, alkaline phosphatase), direct bilirubin, amylase and lipase

Procedures: Bone marrow aspiration and biopsy. Send for standard histology, flow cytometry, cytogenetics (karyotype and *in situ* hybridization for previously documented abnormalities required, other testing per institutional standard of care) and quantitative PCR for BCR-ABL1 p190 and/or p210 if previously positive.

Correlative/exploratory research samples to be collected with bone marrow biopsy and aspirate (See **Section 6.5**)

Adverse Event Assessment

Concomitant Medications

Day 15

Collection of Serum Cytokine Assay samples (See **Section 6.5**) prior to pembrolizumab administration

Administration of Pembrolizumab 200 mg IV once

Vital signs (heart rate and oxygen saturation) to be monitored continuously and full vital signs (temperature, heart rate, blood pressure, respiratory rate, and oxygen saturation) every 4 hours during at least the initial 72 hours of blinatumomab therapy, for 72 hours after all restart or step-up doses, and for at least the initial 72 hours following the first (Cycle 1, Day 15) and third (Cycle 2, Day 15) pembrolizumab doses.

Day 16

Collection of Serum Cytokine Assay Samples 24 hours +/- 2 hour after start of pembrolizumab (See **Section 6.5**)

Day 17

Collection of Serum Cytokine Assay samples 48 hours +/- 2 hours after start of pembrolizumab (See **Section 6.5**)

Day 21

Collection of Serum Cytokine Assay samples (See **Section 6.5**)

Day 28

Administration of Blinatumomab 28 mcg/d CIV days 8-28

Adverse Event Assessment

Concomitant Medications

Day 29 + 8 Days

Labs: CBC with Differential

Procedures: Bone marrow aspiration and biopsy. Send for standard histology, flow cytometry, cytogenetics (karyotype and *in situ* hybridization for previously documented abnormalities only) and quantitative PCR for BCR-ABL1 p190 and/or p210 if previously positive.

MRD assessment: 6-color flow cytometry on bone marrow aspirate on at least 0.5×10^6 mononuclear cells when technically possible. MRD assessment to be done on first pull bone marrow aspirate, redirected bone marrow aspirate should be performed as needed for first pull

bone marrow aspirate. MRD samples to be sent to University of Washington for analysis (**Section 7.1.3, Appendix C**).

Correlative/exploratory research samples to be collected with bone marrow biopsy and aspirate (See **Section 6.5**)

Lumbar puncture with **Methotrexate administration** and CSF studies: Cell count with differential, cytology, and flow cytometry.

Imaging: Diagnostic CT chest, abdomen, and pelvis with IV and oral contrast in patients with palpable lymphadenopathy or masses at diagnosis. Patients unable to get contrasted study should get non-contrasted CT scans.

Adverse Event Assessment

Concomitant Medications

Day 36

Administration of Pembrolizumab 200 mg IV once

Labs: CBC with differential, CMP (sodium, potassium, chloride, bicarbonate, BUN, creatinine, glucose, calcium, total bilirubin, AST, ALT, alkaline phosphatase), direct bilirubin, amylase and lipase

Adverse Event Assessment

Concomitant Medications

Cycle 2

Day 1

Administration of Blinatumomab 28 mcg/d CIV days 1-28

Physical exam, performance status, vital signs, weight

Labs: CBC with differential, CMP (sodium, potassium, chloride, bicarbonate, BUN, creatinine, glucose, calcium, total bilirubin, AST, ALT, alkaline phosphatase), direct bilirubin, amylase and lipase

Adverse Event Assessment

Concomitant Medications

Day 15

Administration of Pembrolizumab 200 mg IV once

Labs: CBC with differential, CMP (sodium, potassium, chloride, bicarbonate, BUN, creatinine, glucose, calcium, total bilirubin, AST, ALT, alkaline phosphatase), direct bilirubin, amylase and lipase

Adverse Event Assessment

Concomitant Medications

Day 29 + 8 Days

Labs: CBC with differential

Procedures: Bone marrow aspiration and biopsy. Send for standard histology, flow cytometry, cytogenetics (karyotype and *in situ* hybridization for previously documented abnormalities required, additional testing allowed per institutional standard of care) and quantitative PCR for BCR-ABL1 p190 and/or p210 if previously positive.

Correlative research samples to be collected with bone marrow aspirate and peripheral blood for flow cytometry and bone marrow aspirate for western blot (See **Section 6.5**)

MRD assessment: 6-color flow cytometry on bone marrow aspirate on at least 0.5×10^6 mononuclear cells when technically possible. MRD assessment to be done on first pull bone marrow aspirate, redirected bone marrow aspirate should be performed as needed for first pull bone marrow aspirate. MRD samples to be sent to University of Washington for analysis (**Section 7.1.3, Appendix C**).

Lumbar puncture with **Methotrexate administration** and CSF studies: Cell count with differential, cytology and flow cytometry.

Imaging: Diagnostic CT chest, abdomen, and pelvis with IV and oral contrast in patients with palpable lymphadenopathy or masses at diagnosis. Patients unable to get contrasted study should get non-contrasted CT scans.

Day 36

Administration of Pembrolizumab 200 mg IV once

Labs: CBC with differential, CMP (sodium, potassium, chloride, bicarbonate, BUN, creatinine, glucose, calcium, total bilirubin, AST, ALT, alkaline phosphatase), direct bilirubin, amylase and lipase

Adverse Event Assessment

Concomitant Medications

Cycles 3 and 4

Day 1

Administration of Blinatumomab 28mcg/d CIV days 1-28

Physical exam, performance status, vital signs, weight

Labs: CBC with differential, CMP (sodium, potassium, chloride, bicarbonate, BUN, creatinine, glucose, calcium, total bilirubin, AST, ALT, alkaline phosphatase), direct bilirubin, amylase, lipase, TSH and T4 (cycles 3 only).

Adverse Event Assessment

Concomitant Medications

Day 15

Administration of Pembrolizumab 200mg IV once

Labs: CBC with differential, CMP (sodium, potassium, chloride, bicarbonate, BUN, creatinine, glucose, calcium, total bilirubin, AST, ALT, alkaline phosphatase), direct bilirubin, amylase and lipase

Adverse Event Assessment

Concomitant Medications

Day 29 + 8 Days

Labs: CBC with differential

Procedures: Bone marrow aspiration and biopsy. Send for standard histology, flow cytometry, cytogenetics (karyotype and *in situ* hybridization for previously documented abnormalities required, additional testing allowed per institutional standard of care) and quantitative PCR for BCR-ABL1 p190 and/or p210 if previously positive.

MRD assessment: 6-color flow cytometry on bone marrow aspirate on at least 0.5×10^6 mononuclear cells when technically possible. MRD assessment to be done on first pull bone marrow aspirate, redirected bone marrow aspirate should be performed as needed for first pull bone marrow aspirate. MRD samples to be sent to University of Washington for analysis (**Section 7.1.3, Appendix C**).

Lumbar puncture with **Methotrexate administration** and CSF studies: Cell count with differential, total protein, random glucose, cytology.

Adverse Event Assessment

Concomitant Medications

Day 36

Administration of Pembrolizumab 200mg IV once

Labs: CBC with differential, CMP (sodium, potassium, chloride, bicarbonate, BUN, creatinine, glucose, calcium, total bilirubin, AST, ALT, alkaline phosphatase), direct bilirubin, amylase and lipase

Adverse Event Assessment

Concomitant Medications

Cycle 5

Day 1

Administration of Blinatumomab 28mcg/d CIV days 1-28

Physical exam, performance status, vital signs, weight

Labs: CBC with differential, CMP (sodium, potassium, chloride, bicarbonate, BUN, creatinine, glucose, calcium, total bilirubin, AST, ALT, alkaline phosphatase), direct bilirubin, amylase, lipase, TSH and T4.

Adverse Event Assessment

Concomitant Medications

Day 15

Administration of Pembrolizumab 200mg IV once

Labs: CBC with differential, CMP (sodium, potassium, chloride, bicarbonate, BUN, creatinine, glucose, calcium, total bilirubin, AST, ALT, alkaline phosphatase), direct bilirubin, amylase and lipase

Adverse Event Assessment

Concomitant Medications

Day 36

Administration of Pembrolizumab 200mg IV once

Labs: CBC with differential, CMP (sodium, potassium, chloride, bicarbonate, BUN, creatinine, glucose, calcium, total bilirubin, AST, ALT, alkaline phosphatase), direct bilirubin, amylase and lipase

Adverse Event Assessment

Concomitant Medications

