5. TREATMENT PLAN

5.1 Treatment dosage and administration

5.1.1 Treatment summary

The study will be conducted in 2 stages:

Stage 1 is to ensure safety of pembrolizumab in combination with blinatumomab.

Dose Limiting Toxicity (DLT) is defined as a clinically significant adverse event that is considered by the investigator to be probably or definitely related to pembrolizumab or the combination of pembrolizumab and blinatumomab occurring within 42 days of the first dose of pembrolizumab on Day 15 of Cycle 1 as follows:

- Any Grade 3-5 non-hematologic toxicity EXCEPT:
 - Grade 3 cytokine release syndrome that resolves in 7 days or less
 - Grade 3 neurotoxicity that resolves in 7 days or less
 - Grade 3 infections
 - Grade 3 or 4 febrile neutropenia unless deemed by investigator to be definitely related to pembrolizumab
 - Grade 3 or 4 laboratory abnormalities unless they warrant temporary discontinuation of pembrolizumab or permanent discontinuation of blinatumomab (see tables, 5.7.1 and 5.7.2)
 - Grade 3 or 4 lymphopenia
- Any clinically significant toxicity that precludes administration of the next scheduled dose for more than 14 days

If no DLTs are experienced in the first 3 subjects then enrollment will advance Stage 2. If 1 DLT is noted in the first 3 subjects then 3 additional subjects will be enrolled. If no further DLTs are noted in the additional 3 subjects then enrollment will proceed to Stage 2. If 2 or more DLTs are noted at the proposed pembrolizumab dose level and schedule then enrollment will be placed on hold and a dose reduction or schedule change will be considered after discussion of investigators.

The DLT monitoring period will be 42 days starting on Day 15 of Cycle 1. Subjects withdrawing from investigational treatment during the DLT monitoring period for a reason that is definitely unrelated to toxicity of the study agent (e.g. disease progression, patient withdrawal of consent) will be deemed not evaluable for DLT determination and will be replaced. All subjects in Stage 1 will need to complete the DLT monitoring period prior to proceeding with Stage 2.

Stage 2 of the study will include an expansion cohort of up to 21 additional subjects (for a total of 24 subjects) to evaluate the efficacy of the combination of blinatumomab and pembrolizumab.

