5.1.3 Therapy

[figure not shown]
Both Stage 1 (safety lead-in) and Stage 2 (dose expansion) of this study will use the same regimen as detailed below.

Schema:

Cycle 1

Cycle 2-5

REGIMEN DESCRIPTION					
CYCLE 1					
Agent	Premedications; Precautions	Dose	Route	Schedule	Cycle Length
Blinatumomab	Dexamethasone 20 mg IV once 1 hour (+/- 30 min) before start of infusion and 1 hour (+/- 30 min) prior to step-up dose on Day 8.	Day 1-7: 9 mcg/day	Continuous IV infusion for 28 days. Bag changes every, 24 hours, 48 hours or 7 days (as appropriate).	Day 1-7	6 weeks (42 days)
		Day 8-28: 28 mcg/day		Day 8-28	
Pembrolizumab	None required, per institutional	200 mg	IV over 30 minutes	Days 15 and 36	

	standard of care				
Methotrexate	None required, per institutional standard of care	15 mg	Intrathecal or intraventricular	Day 29 + 8 days	
CYCLES 2-5					
Blinatumomab	Dexamethasone 20 mg IV once 1 hour (+/- 30 min) before start of infusion.	28 mcg/day	Continuous IV infusion for 28 days. Bag changes every 24hours, 48 hours or 7 days (as appropriate).	Days 1-28	6 weeks (42 days)
Pembrolizumab	None required, per institutional standard of care	200 mg	IV over 30 minutes	Days 15 and 36	
Methotrexate	None required, per institutional standard of care	15 mg	Intrathecal or intraventricular	Day 29 + 8 days	

See **Section 9.1** for details on administration of blinatumomab

Hospitalization requirements:

Cycle 1:

Hospital admission required from day 1 through day 18 and for at least 72 hours after pembrolizumab dose.

Cycle 2:

Hospital admission required day 1-3 for blinatumomab and for at least 72 hours after start of blinatumomab infusion.

Cycles 3-5:

Hospital admission required day 1-3 for blinatumomab and for at least 72 hours after start of blinatumomab infusion.

Hospital admission also required for any blinatumomab restart or step-dose increase and for 72 hours after restart or step-up dose.

Vital signs (heart rate and oxygen saturation) to be monitored continuously and full vital signs (temperature, heart rate, blood pressure, respiratory rate, and oxygen saturation) every 4 hours

during at least the initial 72 hours of blinatumomab therapy, for 72 hours after all restart or step-up doses, and for at least the initial 72 hours following the first (Cycle 1, Day 15) pembrolizumab doses.

CNS Prophylaxis:

Methotrexate 15mg intrathecal or intraventricular at screening, day 29 + 8 days of cycle 1-4, and day 38 +8 days of cycle 5 (end of treatment)

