5.1.4 Stage I – Dose limiting toxicity definition and stopping rules

To determine the safety of pembrolizumab in combination with blinatumomab in patients with acute lymphoblastic leukemia, the combination will be administered to 3-6 patients with relapsed or refractory B-lineage acute lymphoblastic leukemia.

Toxicity will be graded according to the National Cancer Institute (NCI) Common Toxicity Criteria for Adverse Events (CTCAE) version 4.03. Adverse events will be assessed continuously throughout therapy.

Dose Limiting Toxicity (DLT) is defined as a clinically significant adverse event that is considered by the investigator to be probably or definitely related to pembrolizumab or the combination of pembrolizumab and blinatumomab occurring within 42 days of the first dose of pembrolizumab on Day 15 of Cycle 1 as follows:

- Any Grade 3-5 non-hematologic toxicity EXCEPT:
 - Grade 3 cytokine release syndrome that resolves in 7 days or less
 - Grade 3 neurotoxicity that resolves in 7 days or less
 - Grade 3 infections
 - Grade 3 or 4 febrile neutropenia unless deemed by investigator to be definitely related to pembrolizumab
 - Grade 3 or 4 laboratory abnormalities unless they warrant temporary discontinuation of pembrolizumab or permanent discontinuation of blinatumomab (see tables, 5.7.1 and 5.7.2)
 - Grade 3 or 4 lymphopenia
- Any clinically significant toxicity that precludes administration of the next scheduled dose for more than 14 days

Decision to proceed to Stage 2 of the study will be made as follows below.

Number of Patients with DLT	Decision Rule
0 out of 3	Proceed to Stage 2 of study.
1 out of 3	Enter at least 3 more patients. 
 If 0 of these 3 patients experience DLT, proceed to Stage 2 of study If 1 or more of this group suffer DLT, then study will be placed on hold. Decision regarding dosing of pembrolizumab and continuation of study will be made after discussion between sponsors and investigators.
≥ 2	Study will be placed on hold and the FDA notified. Decision regarding dosing of pembrolizumab and continuation of study will be made after discussion between sponsors, investigators and FDA.
≤ 1 out of 6	Proceed to Stage 2 of study.

Subjects withdrawing from investigational treatment during the DLT monitoring period for a reason that is definitely unrelated to toxicity of the study agent (e.g. disease progression, patient withdrawal of consent) will be replaced.

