10.4 Evaluable Subjects and Subject Replacement

Stage 1 (Safety evaluation)

Evaluable subjects are defined as any patient receiving the combination of blinatumomab and pembrolizumab starting day 15 of Cycle 1. The DLT monitoring period will be 28 days starting Day 15 of Cycle 1. Subjects withdrawing from investigational treatment during the 28 day DLT monitoring period for a reason that is definitely unrelated to toxicity of the study agent (e.g. disease progression, patient withdrawal of consent) will be replaced for the safety analysis. 3-6 patients will be enrolled at in Stage 1 as determined by 3+3 rules. These patients will also be evaluated for efficacy.

Stage 2

Stage 2 of the study will include an expansion cohort of up to 21 additional subjects for a total of 24 subjects to evaluate the efficacy of the combination of blinatumomab and pembrolizumab. All patients receiving combination therapy starting day 15 of cycle 1 will be considered evaluable for overall response rate of entire population, RFS and OS.

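### No chemistry is scheduled for the first 21 days of the DLT window (Cycle 1 Days 15 to 35), so a laboratory-defined DLT that resolves before Day 36 can be missed

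*Combined protocol and SAP*

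**What the plan says.** **What counts as a DLT.** Section 5.1.4 (and 5.1.1 in the same terms) defines a DLT as a clinically significant event, judged at least probably related to pembrolizumab or the combination, "occurring within 42 days of the first dose of pembrolizumab on Day 15 of Cycle 1". Among the exceptions to the Grade 3-5 non-hematologic criterion it lists "Grade 3 or 4 laboratory abnormalities unless they warrant temporary discontinuation of pembrolizumab or permanent discontinuation of blinatumomab". Laboratory abnormalities that do lead to those actions are therefore DLTs.

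**How long the window is.** Section 5.1.1: "The DLT monitoring period will be 42 days starting on Day 15 of Cycle 1". Section 10.4: "The DLT monitoring period will be 28 days starting Day 15 of Cycle 1". The two conflict.

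**What is drawn in Cycle 1 (Section 6.2).**

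| Cycle 1 day | Blood tests listed |
|---|---|
| 14 | CBC and a chemistry panel ending in "glucose, calcium, total bilirubin, AST, ALT, alkaline phosphatase), direct bilirubin, amylase and lipase" |
| 15, 16, 17 | Cytokine research samples only, e.g. "Collection of Serum Cytokine Assay Samples 24 hours +/- 2 hour after start of pembrolizumab" |
| 21 | Cytokine research sample only |
| 28 | None; adverse events and concomitant medications only |
| 29 + 8 | "Labs: CBC with Differential", plus research samples |
| 36 | CBC and the same chemistry panel as Day 14 |

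The flow chart in the Study Summary agrees: its rows for the metabolic panel, direct bilirubin, amylase and lipase are blank for Cycle 1 Days 15, 28 and 29 + 8.

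**Other surveillance.** Section 5.1.3: "Hospital admission required from day 1 through day 18"; it specifies vital signs for that stay but no laboratory tests. Section 10.5.1 has the first 6 patients monitored for DLTs every other week.

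**The concern.** The last scheduled chemistry before the combination starts is one day before the first pembrolizumab dose, and the next is three weeks after it. Blinatumomab is infused until Day 28, and admission is required only through Day 18. Immune hepatitis and nephritis, which Section 5.7.1 manages by grade, are detected largely by chemistry, and Section 9.1 lists transaminitis as a blinatumomab side effect. The Day 29 + 8 CBC does not fill the gap, because the graded DLT criterion is non-hematologic.

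The decision to open Stage 2 rests on 3 to 6 patients, so one unrecorded DLT can change it. If early chemistry is left to local practice, ascertainment may also differ among the four centers.

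**Working it through.** There is no stated figure to reproduce, because the point concerns the visit schedule.

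**1. Scheduled chemistry on a study-day axis.** Cycles last 42 days (Section 5.1.3), so Cycle 2 Day 1 is study Day 43 and Cycle 2 Day 15 is study Day 57. Chemistry falls on study Days 1, 14, 36, 43 and 57.

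- Gap: 36 − 15 = 21 days (Days 15 to 35).
- 42-day window: 21/42 = 50%. Days 36 and 43 lie inside. Day 57 is exactly 42 days after Day 15 and is inside or outside depending on how the boundary is counted.
- 28-day window: 21/28 = 75%. Day 36 lies inside, and Day 43 is on the boundary.

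**2. Whether another provision requires a draw in the gap.**

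- The check for events of clinical interest before each dose (Section 8.8.1.2) adds nothing, since the Cycle 1 pembrolizumab doses are on Days 15 and 36.
- Continuous adverse-event assessment (Sections 5.1.4 and 6.2) has no draw attached.
- A two-weekly DLT review (Section 10.5.1) must fall at least once in any 21-day stretch. In this one it has no new scheduled chemistry to look at.

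**3. Which events are exposed.** An abnormality that starts on Days 15 to 35 and is still present on Day 36 is found at the scheduled draw, late but inside either window. Only one that starts and resolves before Day 36, without prompting unscheduled testing, goes unrecorded.

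**4. Illustration for the 3+3 rule.** The rule passes with 0 of 3 DLTs, or with 1 of 3 followed by 0 of 3. With p the probability that a patient has an observed DLT:

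P(pass) = (1 − p)³ + 3p(1 − p)² × (1 − p)³

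Take a true rate of 0.30, the threshold in Section 10.5.1. The documents give no missed-DLT rate, so every missed rate below is assumed. The 0.007 is the sum of the only related rates in the protocol, from the 411 melanoma patients in Section 1.2.2: Grade 4 hepatitis 0.2% plus Grade 3-4 nephritis 0.5%.

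| Missed (absolute) | Share of DLTs missed | Observed p | P(pass) |
|---|---|---|---|
| 0 | 0% | 0.300 | 0.343 + 0.151 = 0.494 |
| 0.007 | 2.3% | 0.293 | 0.353 + 0.155 = 0.509 |
| 0.03 | 10% | 0.270 | 0.557 |
| 0.05 | 16.7% | 0.250 | 0.422 + 0.178 = 0.600 |
| 0.075 | 25% | 0.225 | 0.654 |
| 0.15 | 50% | 0.150 | 0.814 |

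**The case against.** The strongest case against is that few events can slip through.

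- **Definition.** A DLT must be clinically significant and at least probably related, and most isolated laboratory findings are excepted. No pembrolizumab dose is due between Days 15 and 36, so it is unclear whether a silent abnormality that resolves in between warrants a temporary discontinuation at all. Where the tables in Section 5.7.1 require permanent discontinuation, as for Grade 3 immune hepatitis or nephritis, they also plan steroid tapers of at least 4 weeks after resolution. Such events are unlikely to come and go unseen within 21 days.
- **Other surveillance.** Patients are in hospital through Day 18, adverse events are assessed on Days 28, 29 + 8 and 36 and collected continuously, and Section 8.8.1.2 anticipates unscheduled laboratory tests. DLT monitoring also continues at 12 and 24 patients.

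Much of this stands. It makes a missed event less likely and limits how much weight the point can bear. It does not remove the gap: none of these provisions requires chemistry between Days 15 and 35, and an asymptomatic rise in enzymes or creatinine is not found by asking about symptoms. The later DLT looks rely on what was recorded in the same patients. A Grade 3 hepatitis or nephritis meeting the attribution rule would count as a DLT even if it had resolved by Day 36.

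A reader might infer that any laboratory-defined DLT in the first three weeks depends wholly on unscheduled testing. The documents do not support that, because the scheduled Day 36 draw finds whatever persists.

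**Conclusion.** The gap is real, and the procedures text and flow chart agree on it: no scheduled chemistry for 21 days from the first dose of the combination, which is half of the 42-day window or three quarters of the 28-day one. The consequence is later detection of persistent abnormalities and possible loss of transient ones.

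The size of the effect on the Stage 1 decision is unknown. A reader might take the rise in pass probability from 0.494 to 0.60 as the cost of the gap. That figure requires one sixth of all DLTs to be transient, unseen laboratory events in three weeks, and nothing in the documents supports that share. The 0.007 case gives about 0.51, but it is an assumption too. It uses pembrolizumab monotherapy rates in melanoma, which may be too low for the combination, and treats every such event as falling in the gap and being missed, which is too pessimistic. The point rests on the schedule and on the need for uniform ascertainment in 3 to 6 patients, not on either probability.

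**What to change.** Reconcile the Cycle 1 laboratory schedule in Section 6.2 and the flow chart with the DLT window and the every-other-week DLT review in Section 10.5.1. Add the chemistry panel already used on Days 14 and 36 at two existing contacts:

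- **Day 21**, as a separate tube at the blood draw. The cytokine sample cannot serve, because Section 6.5.1.4 has it collected in EDTA, spun and stored at −70C for batch shipment.
- **The Day 29 + 8 visit.** This adds information only if it falls before Day 36, since the visit can be as late as Day 37. The longest interval between scheduled panels would fall from 22 days (Day 14 to Day 36) to 8 days if the visit is on Day 29 (Days 14, 21, 29, 36), or to 15 days (Day 21 to Day 36) if it is on Day 36 or later.

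Also reconcile the 42-day window (Sections 5.1.1 and 5.1.4) with the 28-day window (Section 10.4), and state whether the last day includes the chemistry draw that falls on the boundary.

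Cost: one or two extra tubes per patient and no new visit. The change concerns how the DLT endpoint is measured; it alters no dose, DLT definition or stopping rule.
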